6.4.4. Secondary Analysis of Antibody-Mediated Immunogenicity Endpoints

For Part E, immune response to ancestral SARS-CoV-2 and circulating variants for concern after a single booster dose of 100 µg mRNA-1273.213 will be summarized descriptively.

The mixed effect model repeated measure (MMRM) will be used to analyze all post-booster measures for between booster comparisons (Part G, and Part H) when analyzing immunogenicity data at Month 6 and Month 12 (if applicable), the model will include treatment group, analysis visit, treatment by visit interaction, and adjusting for age groups and pre-booster titer levels, and pre-booster SARS-CoV-2 status when applicable (i.e. using Per-Protocol Immunogenicity Set). An unstructured covariance structure will be used to model the within-participant errors. A Kenward-Roger approximation will be used for the denominator degrees of freedom. If the model does not converge, a compound symmetry covariance structure will be used. The GMT will be estimated from the model and its corresponding 95% CI will be provided for each group at each post-boost timepoint. The GMR (ratio of GMTs) will be estimated from the model and the corresponding 95% CI will be provided at each post-boost timepoint.

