8.5.3.2. Other Analyses of Immunogenicity Applicable to All Study Parts

SARS-CoV-2-specific bAb and nAb are assessed at multiple timepoints in each part of this study.

For each of the antibodies of interest, eg, levels of SARS-CoV-2-specific bAb and SARS-CoV-2-specific nAb, the GMT or level with corresponding 95% CI at each time point, and GMFR of post-baseline/baseline titers or levels with corresponding 95% CI at each post-baseline time point will be provided for each arm. The 95% CIs will be calculated based on the t-distribution of the log-transformed values then back-transformed to the original scale for presentation. The following descriptive statistics will also be provided at each time point: number of participants (n), median, minimum, and maximum.

The MMRM will be used to analyze all postbooster measures for between booster comparison when applicable, the model will include treatment group, analysis visit, treatment by visit interaction, and adjusting for age groups and prebooster titer levels. An unstructured covariance structure will be used to model the within-participant errors. The GMT will be estimated from the model and its corresponding 95% CI will be provided for each group at each postboost timepoint. The GMR (ratio of GMTs) will be estimated from the model and the corresponding 95% CI will be provided at each postboost timepoint.

The SRR of each arm against ancestral SARS-CoV-2 and variants, defined as the percentage of participants achieving seroresponse against ancestral SARS-CoV-2 and variants respectively, will be provided for each arm with the 95% CI calculated using the Clopper-Pearson method.

The primary definition of seroresponse is defined as $\geq 4 \times \text{LLOQ}$ for those with pre-dose 1 of primary series baseline $< \text{LLOQ}$; ≥ 4 -foldrise for those with pre-dose 1 of primary series baseline $\geq \text{LLOQ}$. The secondary definition of seroresponse is defined as $\geq 4 \times \text{LLOQ}$ for those with prebooster baseline $< \text{LLOQ}$; ≥ 4 -foldrise for those with prebooster $\geq \text{LLOQ}$. SRR will be summarized using both definitions for all the study parts.

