4.4. Randomization

Randomization will be performed for participants in Part J. For Part J, participants will be randomized in a 1:1 ratio to receive one of 2 treatments. Randomization will not be blinded.

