
- If non-inferiority is demonstrated for both B.1.1.529 (based on GMR and SRR) and ancestral SARS-CoV-2 (based on GMR), the lower bound of 97.5% CI of GMR will be compared to 1, if it's greater than 1, then superiority against B.1.1.529 is demonstrated.

Analyses for the primary immunogenicity endpoints may also be performed using Per-Protocol Immunogenicity Set.

Day 91: alpha=0.025 (2-sided)

Hypotheses testing at Day 91 will be performed in the same manner, first test two non-inferiority hypotheses (two against the B.1.1.529 strain and one against ancestral SARS-CoV-2) at alpha of 0.025 level (two-sided). Once non-inferiority is demonstrated for both B.1.1.529 and ancestral SARS-CoV-2, then superiority testing against the B.1.1.529 at alpha of 0.025 level (two-sided) will be performed.

For the key secondary objective, hypotheses to be tested (Day 29 and Day 91 each with alpha level of 0.025, 2-sided) are described in [Section 4.2](#). If the lower bound of the 97.5% CI of the SRR difference (50 µg mRNA-1273.214 against the ancestral SARS-CoV-2 - 50 µg mRNA-1273 against ancestral SARS-CoV-2) is >-10% at Day 29 or Day 91, then key secondary objective will be considered met.

In the event that an early assessment of the 1273.214 data is needed due to public health concerns, a two-staged approach will be used. Specifically, a subset of participants' (ie, 50 first enrolled participants) serum samples will first be tested against ancestral SARS-CoV-2 and various VOCs. For the Day 29 and Day 91 immunogenicity analyses, all participants' immune data will be used in the formal analysis to evaluate the primary immunogenicity objective.

Part H

Primary analysis set for immunogenicity objectives will be based on PPIS-Neg.

50 µg mRNA-1273.222 as the second booster dose will be compared to 50 µg mRNA-1273 as the second booster dose (active control arm in Part F, Cohort 2).

Study Part H was enrolled in August 2022 and Part F 50 µg mRNA-1273 was enrolled in February 2022, baseline and demographic characteristics will be examined between the two study parts before comparing immunogenicity data.

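### As written, the Part G and Part H MMRM fits one pre-booster titre slope to all visits, which can bias the secondary GMRs if the non-randomised arms differ in pre-booster titre and the slope changes over time

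*SAP*

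**What the plan says.** SAP 6.4.4 specifies an MMRM for the between-booster comparisons in Parts G and H when Month 6 and, where it exists, Month 12 data are analysed: "the model will include treatment group, analysis visit, treatment by visit interaction, and adjusting for age groups and pre-booster titer levels". Pre-booster SARS-CoV-2 status is added when the wider per-protocol set is used. Protocol 8.5.3.2 carries the same list: "the model will include treatment group, analysis visit, treatment by visit interaction, and adjusting for age groups and prebooster titer levels". On covariance the SAP says "An unstructured covariance structure will be used to model the within-participant errors". The model reports a GMR with a 95% CI at every post-boost time point, so it yields a Day 29 GMR as well as the later ones.

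On how the arms arise, SAP 4.4 says "Randomization will be performed for participants in Part J", and no other part is randomised. SAP 4.1 has Part G start enrolling once the Part F Cohort 2 mRNA-1273 arm is full. For Part H, SAP 6.4.3 records that "Study Part H was enrolled in August 2022 and Part F 50 µg mRNA-1273 was enrolled in February 2022" and that "baseline and demographic characteristics will be examined between the two study parts before comparing immunogenicity data". It states no consequence of that examination for the MMRM.

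**The concern.** Only treatment is allowed to have a different effect at each visit. Pre-booster titre enters as a plain covariate, so its slope is one number shared by Day 29 and the later visits. If the true slope differs between the peak and the later phase, the shared slope over-adjusts at one end and under-adjusts at the other.

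In a randomised comparison this costs little, because the arms share the same expected baseline. Here nothing ensures that. The arms were enrolled in sequence, and inclusion criterion 6 sets only a minimum of 3 months since the previous booster, so time since boosting can differ. The negative-at-baseline analysis set removes participants with evidence of infection but does not balance titre. Any slope misfit is then multiplied by the arm difference in baseline titre and passes into the GMR at each visit. Because the error changes sign between early and late visits, it could distort the apparent durability of the difference between boosters.

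**Working it through.** **Inputs from the documents.** Part H: 300 versus 260 participants. Part G: 300 versus 300. SD of log titre 1.5 (SAP 4.3). Post-boost neutralising visits (SAP Table 3): Days 29 and 181 for Part H; Days 29, 91, 181 and 366 for Part G and its comparator.

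**The plan's own figures.** None is stated for the MMRM. The stated powers do reproduce if the SD of 1.5 is on the natural-log scale and superiority is included. Part G: SRR 0.967 × ancestral GMR 0.8575 × superiority 0.8575 = 0.711 (stated 71%). Part H: 0.773 × 0.891 × 1.000 × 0.891 = 0.613 (stated 60%). Natural logs are used below.

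**Inputs that are assumptions.** The titre slopes, the arm ratio of pre-booster GMTs, the residual SD and the between-visit correlation are not in the documents.

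**Formula.** Let b_v be the true slope at visit v and S the residual covariance. The fitted common slope tends to b_c = (1′S⁻¹b)/(1′S⁻¹1). The bias in log GMR at visit v is (b_v − b_c) × δ, where δ is the arm difference in mean log pre-booster titre. It is zero if δ = 0 or if all b_v are equal.

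**Part H, slopes 0.3 (Day 29) and 0.6 (Day 181).** Assume residual SD 1.2 at both visits, correlation 0.6, baseline SD 1.5.

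- b_c = (0.3 + 0.6)/2 = 0.45, so the misfit is ±0.15.
- SE ≈ 1.2 × √(1/300 + 1/260) = 0.102.
- 1.5-fold difference: 0.15 × ln 1.5 = 0.061, so the GMR is multiplied by 1.06 at one visit and 0.94 at the other. Shift 0.061/0.102 = 0.60 SE; coverage Φ(1.36) − Φ(−2.56) ≈ 91%. Simulated: 90–93%.
- 2-fold difference: 0.15 × ln 2 = 0.104, factors 1.11 and 0.90. Shift 1.02 SE; coverage ≈ 82%. Simulated: 83–85%. The hand figure is slightly low because it omits slope uncertainty and the misfit's own residual variance, which widen the interval.
- With a titre-by-visit term: GMR about 1.00 (true value 1), coverage 94–96%.

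**Part H, slopes falling from 0.6 to 0.4.** Assume total and baseline SD 1.5, correlation 0.7, true GMR 1.5. Residual variances are 2.25 × (1 − 0.36) = 1.44 and 2.25 × (1 − 0.16) = 1.89, with covariance 0.7 × √(1.44 × 1.89) = 1.155. The weights are proportional to 0.735 and 0.285, so b_c = 0.544, as simulated. At a 2-fold ratio, Day 181 is 1.5 × exp(−0.144 × 0.693) = 1.36.

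Simulated Day 181 results, common-slope model, 1,000 runs per case:

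| Slopes (Day 29 / Day 181) | Baseline ratio | Mean GMR (true 1.5) | Coverage |
|---|---|---|---|
| 0.5 / 0.5 | up to 3 | 1.50–1.51 | 94.9–95.8% |
| 0.6 / 0.4 | 1.25 | 1.46 | 94.5% |
| 0.6 / 0.4 | 1.5 | 1.42 | 92.6% |
| 0.6 / 0.4 | 2 | 1.36 | 87.1% |
| 0.7 / 0.3 | 1.5 | 1.29 | 78.2% |

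Day 29 moves the other way: for 0.6/0.4 and a 2-fold ratio it is 1.56, with 94.0% coverage.

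**Part G, slopes 0.6/0.5/0.4/0.3, true GMR 1.5, 600 runs per case.** At a 1.25-fold ratio the Day 366 GMR is 1.43 (coverage 93.8%); at 1.5-fold, 1.39 (90.8%); at 2-fold, 1.32 (81.2%), with Day 29 at 1.63 (87.7%).

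With the interaction, every completed case in both parts gave 1.49–1.51 and coverage of 93.5–97.5%. Limits: data were complete, and Wald intervals stood in for Kenward-Roger, which is close at 560–600 participants.

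**The case against.** The strongest reply is that two things must hold together, a titre difference between arms and a slope that changes over time, and the documents establish neither. Rising and falling slopes give opposite signs for the same imbalance, so even the direction is unknown. At a 1.25-fold ratio with slopes 0.6/0.4, Day 181 coverage is 94.5%. In the 0.3/0.6 case a 1.5-fold difference gives a bias of 0.061 against a half-width of 1.96 × 0.102 = 0.20, under a third of it. Censoring at off-study vaccination would shrink the later samples and widen the intervals, so the same bias would cost less coverage. For Part G no enrolment gap is stated beyond the sequence itself. All of this stands and makes the point conditional.

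It can also be said that the wording on adjustment does not strictly exclude a visit-specific titre effect, and that SAP 6.4.5 reports each arm's GMT and GMFR without this model. Neither removes the problem. A plan that names one interaction will normally be programmed with that one alone, and per-arm summaries do not replace the adjusted between-arm GMR.

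A reader might infer that the primary conclusions are at risk. They are not. The formally tested GMRs at Day 29 and, in Part G, Day 91 come from an ANCOVA at a single visit with its own titre slope, and no alpha or success criterion attaches to the MMRM.

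**Conclusion.** The point holds in conditional form. As written, the MMRM fits one pre-booster titre slope to all visits in comparisons where baseline balance is not assured. Under the assumed 0.3/0.6 slopes, the Part H GMRs are off by about 6% at a 1.5-fold baseline difference and about 11% at 2-fold, with coverage of 90–93% and 83–85%. Other assumed slopes give smaller or larger errors, and with equal slopes or equal baselines there is none.

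The reach is limited to the secondary MMRM GMRs: Days 29 and 181 in Part H, and visits through Day 366 in Part G. Part H has no Month 12 visit. The SRR differences do not come from this model. A reader might go further and conclude that the late GMRs are in fact biased, or that an apparent waning pattern would be an artefact. The documents do not support that, since they give neither the baseline titre difference nor the slopes. The change is still worth making, because the exposure is avoidable at almost no cost.

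**What to change.** Add a pre-booster-titre-by-visit interaction to the MMRM in SAP 6.4.4 and protocol 8.5.3.2, and leave the rest of the model unchanged.

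The cost is one extra parameter in Part H (two post-boost visits) and up to three in Part G (four visits). Precision is barely affected. Take Part H with equal slopes, residual SD 1.2, correlation 0.6, baseline SD 1.5 and a 2-fold difference, so δ² = 0.48. The variance without slope uncertainty is 1.44 × (1/300 + 1/260) = 0.01034. A common slope adds 0.48 × [1.44 × (1 + 0.6)/2]/(560 × 2.25) = 0.00044, giving SE 0.1038. A slope per visit adds 0.48 × 1.44/(560 × 2.25) = 0.00055, giving SE 0.1044. That is under 1% wider.

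An age-group-by-visit term is optional; nothing here shows that it is needed.

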6.4.5. Exploratory Analysis of Antibody-Mediated Immunogenicity Endpoints

For each booster arm, the following evaluations will be performed at each time point at which blood samples are tested for immunogenicity (unless otherwise specified).

- In relation to the immune response of each booster arm to other SARS-CoV-2 viral variants, the GMT, geometric mean fold rise (GMFR) and seroresponse rate will be calculated at the time points where the immune response is assessed for such variants.
- For each antibody of interest, the GMT or level with corresponding 95% CI at each time point will be provided. The 95% CIs will be calculated based on the t-distribution of the log-transformed values then back-transformed to the original scale for presentation. The following descriptive statistics will also be provided at each time point: number of participants (n), median, minimum, and maximum.

- For each antibody of interest GMFR of post-baseline titers or levels over baseline with their corresponding 95% CIs at each post-baseline time point will be provided. The 95% CIs will be calculated based on the t-distribution of the log-transformed values then back-transformed to the original scale for presentation. The following descriptive statistics will also be provided at each time point: number of participants (n), median, minimum, and maximum.
- For each antibody of interest, the proportion of subjects with fold-rise ≥ 2 , fold-rise ≥ 3 , and fold-rise ≥ 4 from baseline at each post-injection time point will be tabulated with 95% CI calculated using the Clopper-Pearson method.
- Seroresponse rate of each booster arm against the ancestral SARS-CoV-2 and variants, defined as the percentage of participants achieving seroresponse against the ancestral SARS-CoV-2 strain and variants respectively, will be provided with the 95% CI calculated using the Clopper-Pearson method.

6.4.6. Sensitivity Analysis

Sensitivity analysis for the immunogenicity endpoints may be performed with the same methods described above based on the PP Immunogenicity Sensitivity Set.

Sensitivity analysis may be performed for the primary immunogenicity endpoints by excluding all records after SARS-CoV-2 infection.

Additional sensitivity analysis may be performed to assess robustness of the primary immunogenicity analysis results for GMR if more than 10% immunogenicity data are missing at Day 29 or Day 91 (Part G) in the Per-Protocol Immunogenicity Set. Multiple imputation will be used to impute for missing antibody titer data. Following steps outline multiple imputation process and subsequent analysis.

Step 1: We will assume antibody titer data follows a log normal distribution.

- Markov Chain Monte Carlo (MCMC) will be used for imputation, imputation model will include treatment group, pre-booster baseline titer, age group, Day 29/ Day 91 (when applicable) titer data in log scale (with a base of 10). Each missing data point will be filled with a set of imputed values.

Step 2: Generate a set of datasets with imputed antibody titer values.

Step 3: Each complete dataset will be analyzed using ANCOVA model with treatment group as a fixed effect, adjusting for pre-booster baseline tier, and age group. Each model will estimate GMR (between treatment group comparison) and standard error in Log 10 scale.

Step 4: The results from these analyses will be combined into a single estimate using [Rubin's \(1987\)](#) method, the combined estimate will be transformed back to original scale for presentation.

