4.5. Blinding and Unblinding

Not applicable.

4.6. External Comparator for Part F Cohort 1 - Study mRNA-1273-P201 Part B Subjects

Study mRNA-1273-P201 (P201) Part B, is the Open-Label Interventional Phase of the study, and was prompted by the authorization of a COVID-19 vaccine under an EUA. In Part B, all participants who previously received 1 or 2 injections of mRNA-1273 (50 µg or 100 µg) vaccine were able to receive a single booster dose of mRNA-1273 (50 µg). A total of approximately 150 participants in the P201 50 µg mRNA-1273 booster arm who were primed with 2 doses of 100 µg mRNA-1273 will serve as an external comparator for the P205 Part F 50 µg mRNA-1273.529 arm (Cohort 1).

5. Analysis Sets

The following analysis sets are defined: All Enrolled Set, Full Analysis Set, Per-Protocol Immunogenicity Set, Per-Protocol Immunogenicity Sensitivity Set, Per-Protocol Immunogenicity SARS-CoV-2 Negative Set, Solicited Safety Set, Safety Set, and Per-Protocol Efficacy Set. Definitions are the same across study Parts A (1, 2), B, C, D, E, F, G, H and J when applicable.

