5.3. Per-Protocol Immunogenicity Set (PPIS)

The Per-Protocol Immunogenicity Set (PPIS) for immunogenicity consists of all P205 participants in the FAS who meet all the criteria listed below, and who were in P201 external comparator who were in the Per-Protocol Set for Part B.

mRNA-1273-P205 participants

- a) Received the planned dose of study vaccination per schedule
- b) For Parts A.1, A.2, B, C, D, F, G, H: had pre-booster and Day 29 (occurring between 21 and 42 days after vaccination) neutralizing antibody data; for Part J: had pre-booster and Day 15 neutralizing antibody data
 - Part A.1: against B.1.351 variant
 - Part A.2: against B.1.1.529 variant
 - Part B: against ancestral SARS-CoV-2
 - Part C: against B.1.617.2 variant
 - Part D: against B.1.351 variant and B.1.617.2 variant
 - Part F (Cohort 1 and Cohort 2): against B.1.1.529 variant
 - Part G: against B.1.1.529 variant
 - Part H: against BA.4/5 variant
 - Part J: against XBB.1.5 variant
- c) Had no major protocol deviations that impact key or critical data
- d) Had no previous HIV infection

mRNA-1273-P201 external comparator

Consists of P201B participants after 100 µg primary series who were in Per-Protocol Set for Part B (please refer to P201 SAP version 5.0 Section 5.6 for details).

The PPIS will be used as the primary analysis set for analyses of immunogenicity for Parts A.1, B, C, D, and J, Full Analysis Set will be used for Part E binding antibody descriptive summary.

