5.4. Per-Protocol (PP) Immunogenicity Sensitivity Set

For Parts A.1, A.2, B, C, D, F, G, H, the PP Immunogenicity Sensitivity Set for immunogenicity may be used for sensitivity analysis and will consist of participants who meet all requirements for the PPIS with the exception of the time window for Day 29 neutralizing antibody data.

mRNA-1273-P205 participants

- a) Received the planned dose of study vaccination per schedule
- b) Had pre-booster and Day 29
 - Part A.1: against B.1.351 variant
 - Part A.2: against B.1.1.529 variant
 - Part B: against ancestral SARS-CoV-2
 - Part C: against B.1.617.2 variant
 - Part D: against B.1.351 variant and B.1.617.2 variant
 - Part F (Cohort 1 and Cohort 2): against B.1.1.529 variant
 - Part G: against B.1.1.529 variant
 - Part H: against BA.4/5 variant
- c) Had no major protocol deviations that impact key or critical data
- d) Had no previous HIV infection

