- Part F Cohort 2: 50 µg of mRNA-1273.529 and 50 µg of mRNA-1273
- Part G: 50 µg of mRNA-1273.214
- Part H: 50 µg of mRNA-1273.222
- Part J: 50 µg of mRNA-1273.815 and 50 µg of mRNA-1273.231

External comparator

- 50 µg of mRNA-1273 (booster arm primed with 2 doses of 100 µg mRNA-1273 from Study mRNA-1273-P201 used as an external comparator for P205 Part F Cohort 1).

Subgroup Analysis

Immunogenicity will be assessed in the following subgroups:

- Age (18 to <65, and ≥ 65 years)

- Sex (female, male)
- Pre-booster SARS-CoV-2 status (negative, positive) if there is enough of pre-booster positives
- Race (White, Black or African American, Other)
- Ethnicity (Hispanic or Latino, Not Hispanic or Latino)

Safety may be assessed for the same subgroups.

Subgroup analyses may not be performed for Part J due to small sample size.

Analyses Approach

There are multiple parts in P205, all analyses and data summaries/displays will be provided by study arm for each study part using appropriate analysis population.

Subjects Received Off-study COVID-19 Vaccine

If a participant received off-study COVID-19 vaccine, the participant's immune response and effectiveness data will be censored at the earlier date of date of off-study COVID-19 vaccine, or date of last observed in study.

All analyses will be conducted using SAS Version 9.4 or higher.

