6.4.1. Immunogenicity Assessments

Blood samples for immunogenicity assessments will be collected at the time points indicated in the SoE table in the protocol. Immunogenicity assessments that were tested and applicable for analysis are displayed in [Table 3 for neutralizing antibody assessment](#). Binding antibody were also assessed at the same timepoints.

Table 3: Neutralizing antibody assessments tested by part, dose, time point, and variant

	Dose	D1	D15	D29	D91	D181	D366
Part A.1	.211 50 µg	D614G/ .351/ .617/ BA.1		D614G/ .351/ .617/ BA.1	N/A	D614G/ .351/ .617/ BA.1	Not done
	.211 100 µg	D614G/ .351/ .617		D614G/ .351	N/A	D614G/ .351	Not done
Part B	1273 100 µg	D614G/ .617/ .351		D614G/ .617/ .351	N/A	Not done	Not done
Part C	.617 50 µg	D614G/ .617		D614G/ .617	N/A	Not done	Not done
	.617 100 µg	D614G/ .617		D614G/ .617	N/A	Not done	Not done
Part D	.213 50 µg	D614G/ .617/ .351		D614G/ .617/ .351	N/A	Not done	Not done
	.213 100 µg	D614G/ .617/ .351		D614G/ .617/ .351	N/A	Not done	Not done
Part E	.213 100 µg	D614G		D614G	N/A	Not done	Not done

Part F	.529 Booster 1 50 µg	D614G/ BA.1		D614G/ BA.1	Not done	Not done	Not done
	.529 Booster 2 50 µg (4th dose)	D614G/ BA.1		D614G/ BA.1	Not done	Not done	Not done
	1273 50 µg	D614G/ BA.1		D614G/ BA.1	D614G/ BA.1	D614G/ BA.1	D614G/ BA.1
Part G	.214 50 µg	D614G/ BA.1		D614G/ BA.1	D614G/ BA.1	D614G/ BA.1	D614G/ BA.1
Part H	.222 50 µg	D614G/ BA4.5		D614G/ BA4.5	Not done	D614G/ BA4.5	N/A
Part A.2	.214 50 µg	D614G/ BA.1/ .351		D614G/ BA.1/ .351	Not done	D614G/ BA.1/ .351	N/A
Part J	.231/.815 50 µg	D614G/ BQ1.1/ BA4.5/ XBB1.5	D614G/ BQ1.1/ BA4.5/ XBB1.5	D614G/ BQ1.1/ BA4.5/ XBB1.5	Not done	D614G/ BQ1.1/ BA4.5/ XBB1.5	N/A

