The number and percentage (rate) of participants achieving seroresponse at Day 29 will be summarized with 95% CI calculated using the Clopper-Pearson method for each group. The difference of SRR between mRNA-1273.529 and mRNA-1273 will be calculated with 95% CI based on stratified Miettinen-Nurminen method adjusted for age group. The non-inferiority in SRR of mRNA-1273.529 compared to mRNA-1273 will be considered demonstrated if the lower bound of the 95% of the SRR difference is $> -10\%$ based on the non-inferiority margin of 10%.

The primary immunogenicity objective (against the variant B.1.1.529) is considered met if non-inferiority is demonstrated based on GMR and SRR difference, specifically:

- If the lower bound of the 95% CI of the GMT ratio between mRNA1273.529 against the variant (B.1.1.529) at Day 29 as compared to 50 μ g mRNA1273 against B.1.1.529 at Day 29 is > 0.667 based on the non-inferiority margin of 1.5.

- The lower bound of the 95% CI of the SRR difference (50 µg mRNA-1273.529 against the variant B.1.1.529 at Day 29 - 50 µg mRNA-1273 against B.1.1.529) is > -10%.
- If non-inferiority is demonstrated, the lower bound of 95% CI of the GMT ratio will be compared to 1, if it's greater than 1, then superiority is demonstrated.

A supportive analysis for the primary immunogenicity endpoints may also be performed using Per-Protocol Immunogenicity Set. For immune response against the B.1.1.529 strain, in the ANCOVA model, antibody titers at Day 29 post-booster against the B.1.1.529 strain will be a dependent variable, and a group variable (mRNA-1273.529 and mRNA-1273) will be the fixed effect, adjusting for age groups (< 65, \geq 65 years), pre-booster SARS-CoV-2 status, and pre-booster titer if applicable; the model may also be adjusted for other characteristics. The difference of SRR between mRNA-1273.529 and mRNA-1273 will be calculated with 95% CI based on stratified Miettinen-Nurminen method adjusted for pre-booster SARS-CoV-2 status and age group.

Part F Cohort 2

Primary analysis set for immunogenicity objectives will be based on PPIS-Neg.

50 µg mRNA-1273.529 as the second booster dose will be compared to 50 µg mRNA-1273 as the second booster dose. For the primary objective on immune response for a second booster dose of 50 µg mRNA-1273.529, see [Section 4.2](#). The same analysis methods described for Part F Cohort 1 will be used for the primary immunogenicity objective for Part F Cohort 2.

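### The more-than-10% missing-data trigger cannot register an absent Day 29 B.1.1.529 titre in Part F Cohort 2 or Part G, because entry to the set it counts in already requires that titre

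*SAP*

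**What the plan says.** SAP 6.4.6 (Sensitivity Analysis) allows multiple imputation of titres, to test the robustness of the primary GMR, "if more than 10% immunogenicity data are missing at Day 29 or Day 91 (Part G) in the Per-Protocol Immunogenicity Set". Step 1 specifies that the "imputation model will include treatment group, pre-booster baseline titer, age group, Day 29/ Day 91 (when applicable) titer data in log scale". Appendix F records that the imputation was added in SAP version 3.0 after regulator feedback.

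SAP 5.3 defines the PPIS. Participants in this study must meet every listed criterion, and criterion b is that they "had pre-booster and Day 29 (occurring between 21 and 42 days after vaccination) neutralizing antibody data". The strain named for both Part F cohorts and for Part G is B.1.1.529. SAP 5.5 repeats the criterion for PPIS-Neg, the primary set in Parts F and G. The Part G control is the mRNA-1273 arm of Part F Cohort 2 (SAP 6.4.3).

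Two other reruns are offered:
- SAP 5.4 defines a Sensitivity Set that matches the PPIS "with the exception of the time window for Day 29 neutralizing antibody data".
- SAP 6.4.3 says, under Part F Cohort 1, "A supportive analysis for the primary immunogenicity endpoints may also be performed using Per-Protocol Immunogenicity Set", and makes the same offer for Part F Cohort 2 and Part G.

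**The concern.** A missing-data check should count over the people who could have gone missing. Here a vaccinated participant with no Day 29 B.1.1.529 titre leaves the set before the count is made. For that GMR the rule can neither detect the loss nor supply the lost value.

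The arms in these comparisons were enrolled one after another and not randomised against each other (only Part J is randomised), so equal sample loss cannot be taken for granted. The disposition tables in SAP 6.2.1 will show how many participants fall out of each set. No planned analysis shows what their absence does to the Day 29 GMR. Superiority against B.1.1.529, a listed primary aim in both parts, rests on that complete-case GMR.

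**Working it through.** **The plan's own figures.** Inputs from SAP 4.3: 300 per arm, SD of log titre 1.5, true GMR 1.5, GMR margin 1.5, SRR 90% in both arms, SRR margin 10%. Normal-approximation powers are multiplied as if independent.
- Part F Cohort 2 (two-sided alpha 0.05): GMR non-inferiority 1.000 × SRR 0.9831 × superiority 0.9116 = 0.896, against about 89% stated.
- Part G (alpha 0.025): 1.000 × 0.9672 × 0.8575 (ancestral GMR) × 0.8575 (superiority) = 0.711, against about 71% stated.

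Both reproduce, so the SD of 1.5 is on the natural-log scale.

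**Can the trigger fire?** With 600 in the two arms, 10% is 60, so 61 missing titres are needed. Criterion b allows none, whatever the loss among those vaccinated. With 750 vaccinated, a 10% or 20% loss leaves 675 or 600 in the PPIS, with 0% missing each time. The plan assumes that 20% are excluded from PPIS-Neg (375 × 0.8 = 300) but does not split this by reason. Absent Day 29 titres could be anywhere from 0% to 20% of those vaccinated.

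**Do the other analyses bring these participants back?** The Sensitivity Set relaxes only the window. The PPIS rerun keeps criterion b. The rerun that drops records after infection only removes data. The repeated-measures model in SAP 6.4.4 names no set wider than the PPIS.

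**Illustrative size.** Assumptions not taken from the documents: loss of 5/10/20% in the test arm only; logit(loss) falling by 1 per SD of Day 29 titre; pre-booster correlation 0.5; 1,000,000 simulated per arm; ANCOVA on group and pre-booster titre (age group omitted). True GMR 1.50.

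| Analysis | 5% | 10% | 20% |
|---|---|---|---|
| Complete case | 1.58 | 1.66 | 1.83 |
| Imputed without Day 91 | 1.58 | 1.66 | 1.83 |
| Part G, with Day 91, residual correlation 0.8 | 1.53 | 1.56 | 1.61 |
| Same, correlation 0.5 | 1.56 | 1.62 | 1.74 |
| Same, correlation 0.3 | 1.57 | 1.65 | 1.80 |
| Correlation 0.8, half also lacking Day 91 | 1.56 | 1.61 | 1.72 |
| Equal loss in both arms, complete case | 1.50 | 1.50 | 1.50 |

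If everyone missing Day 29 also lacks Day 91, imputation corrects nothing.

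**Tipping point for superiority.** Observed GMR 1.5, 300 per arm, standard error held fixed:

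ln LB = ln 1.5 − z × SD × √(2/300)

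If a share m of the test arm is absent and its log titres are lower by d, the full-arm log GMR falls by m × d. The fold that removes superiority is therefore exp(ln LB / m). SD 1.5 is unadjusted; SD 1.5 × √0.75 = 1.30 is the ANCOVA residual under the correlation assumed above.
- F Cohort 2, z = 1.960: ln LB = 0.1654 (SD 1.5) or 0.1976 (SD 1.30).
- G, z = 2.241: ln LB = 0.1310 or 0.1677.

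| Fold-lower absent titres needed | 5% | 10% | 20% |
|---|---|---|---|
| F Cohort 2 | 27–52 | 5.2–7.2 | 2.3–2.7 |
| G | 14–29 | 3.7–5.4 | 1.9–2.3 |

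For GMR non-inferiority the fold is exp((ln LB + 0.4055)/m). At m = 0.20 this is 17 to 20 in F Cohort 2 and 15 to 18 in G.

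**The case against.** The case for leaving the text alone has real weight.

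- **The analysis is optional.** SAP 6.4.6 says that it may be performed, and it decides nothing. True, but an optional check should be able to see what it was written to look for.
- **The protocol's PPIS has no titre criterion** (Protocol 8.4, Table 15), and under that definition the trigger would work. However, the SAP introduction says that the SAP prevails where the two differ.
- **The trigger is not dead.** In Part G, neither Day 91 titres nor ancestral titres are entry criteria, so gaps there can fire it. A reader might infer that the rule is useless throughout; the documents do not support that. If strains were pooled, ancestral gaps could even trip it at Day 29, but there would still be no absent B.1.1.529 titre in the set to impute.
- **Censoring could blank a Day 29 titre.** This could happen if censoring after off-study vaccine were applied once set membership was fixed. It would have to affect more than 10% of the set by Day 29.
- **The bias scenario is severe.** It needs loss that differs between arms and depends on the unmeasured Day 29 titre, and no passage documents such loss. A 20% loss would use the whole exclusion allowance. This objection stands, so the sizes above are illustrations.
- **Recovery in Part G depends on assumptions.** It shrinks quickly as the Day 29/Day 91 correlation falls or as the same people miss both visits. This also stands.

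A reader might extend the count to Part F Cohort 1 or Part H. The Cohort 1 comparator enters through a per-protocol set defined in another study's SAP, which is not provided. For Part H, SAP Table 3 lists only D614G and BA.1 for the comparator arm. Neither supports a trigger count or a tipping point.

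**Conclusion.** The point holds for the Day 29 B.1.1.529 GMR in Part F Cohort 2 and Part G. There the trigger sees 0% missing by definition, and participants without the titre are beyond the reach of every sensitivity analysis planned. This follows from the set definitions and needs no numerical assumption.

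The consequence is minor. GMR non-inferiority, part of the rule for meeting the primary objective, would survive absent titres about 15-fold lower even at 20% loss. Superiority is exposed only if loss is both substantial and one-sided: about 2- to 3-fold lower at 20%, 4- to 7-fold at 10%, and 14-fold or more at 5%. A reader might infer that the complete-case GMR is biased. The documents do not show that: they give no loss rate and no evidence of titre-dependent loss, and equal loss leaves the GMR near 1.50.

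**What to change.** In SAP 6.4.6, count missingness by arm, antigen and visit, and impute, among participants who meet all PPIS-Neg criteria except the Day 29 part of criterion b. Treat out-of-window Day 29 titres as observed, as the Sensitivity Set does, and impute only absent ones. Say whether participants whose "immune response and effectiveness data will be censored at the earlier date of date of off-study COVID-19 vaccine" are imputed; Protocol 6.2 collects no scheduled blood from them afterwards.

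In Part G, keep the Day 91 titre in the imputation model; Table 3 shows it tested in both arms. In Part F Cohort 2, Day 91 was not tested in the mRNA-1273.529 arm, so imputing from pre-booster titre and age would essentially return the complete-case GMR. A delta-adjusted run is an optional addition there. Table 3 is written in the past tense ("Immunogenicity assessments that were tested and applicable for analysis are displayed in" it), so if Day 29 results have been seen, the SAP should say so when it sets the delta range.

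The cost is a sentence on the denominator, a sentence on out-of-window and censored participants, and one extra sensitivity run in Part G on existing data. The primary analysis does not change.
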